8.3.2 Measuring Immune Cells

8.3.2.1 Circulating Immune Cells ([name] Laboratory)

A small amount of PBMCs (approximately 3 x 10⁶ cells) from blood draws at Visit 1, Visit 3, and Visit 5 will also be used to monitor levels of circulating immune cells such as Tregs and MDSC to assess whether vaccination may decrease their levels [60]. Flow cytometry will be used to determine the number of CD4+ CD25+ FOXP3+ (Treg) [29] and CD11b+CD14+CD33+IL4R \square +HLA-DR \square neg (MDSC) cells [29, 61, 62]. T-bet (Th1), GATA3 (Th2), and/or ROR gammaT (TH17) positive cells may also be examined. The number of circulating immune cells will be determined before vaccination, after two, and after four injections.

8.3.2.2 Cervical Immune Cells (UAMS Experimental Pathology Core)

After routine pathological diagnosis has been made from LEEP sample obtained at the Optional LEEP Visit, additional sections may be examined for cervical immune cells such as those positive for CD3 (T-cell), CD4 (helper T-cell), CD8 (cytotoxic T-cell), CD56 (NK cell), CD1a (Langerhan cells important in antigen presentation), CD20 (B-cell), CD68 (macrophage), FOXP3 (Treg), T-bet (Th1), and MadCAM-1 (addressing involved with T-cell infiltration). Eosinophils (Th2) may also be examined.

8.3.2.3 Others

Additional analyses that may be performed using blood samples to assess vaccine response include antibody production to HPV proteins, cytokine/chemokine, and metabolomic responses ([name] and Metabolon laboratories).

9 DATA ANALYSIS

9.1 ASSESSING EFFICACY

A historical placebo group, from a previously reported study with a similar study design (i.e., enrollment of subjects with biopsy-proven CIN2/3, and clinical response assessed by biopsy in 15 months), will be used for comparison [57]. The strict definition of histological response which only considers “complete responders” to be “responders” will be used. Those with any CIN remaining would be considered as “non-responders” for the purpose of comparing with the historical placebo group. The response rate in PepCan or Candin® recipients who completed the trial after the 12-

Month-Visit will be compared with that of the historical placebo group which was 29.1% (34 of 117) using binomial test. The response rates between the PepCan and Candin® groups will be compared using the Fisher's exact test. See "Rationale for Primary Outcome Measure: Efficacy" (Section 1.5.9) for power analysis and sample size justification.

In addition to the above analysis of subjects who exited after the 12-Month Visit, another analysis may be performed with addition of subjects who exited the study after the 6-Month Visit if histological results (biopsy and/or LEEP) are available at 6 months. As 21 patients in the placebo arm were removed from the study at 3 or 6 months for having persistent biopsy-proven CIN3 [57], the response rate of 24.6% (34 of 138) will be used for this comparison.

For an intention-to-treat analysis, all subjects who qualified for vaccination will be included regardless of whether any vaccinations were received. In the historical placebo group, 149 subjects were randomized and qualified for vaccination [57]. Therefore, the placebo response rate for this analysis will be 22.8% (34 of 149).

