2 OBJECTIVES

2.1 PRIMARY OBJECTIVE: EFFICACY

To assess the efficacy of PepCan and Candin® in a Phase II clinical trial by determining clinical response which will be assessed by obtaining colposcopy-guided quadrant biopsies at the 12-Month Visit. Responses will be compared between (1) the PepCan group and a historical placebo group [57], (2) the Candin® group and the same historical placebo group, and (3) the PepCan and Candin® groups. If, upon the 12-Month Visit quadrant biopsies, a subject does not have any evidence of CIN, she would be considered a “complete responder”. If the lesion(s) has(have) regressed to CIN 1, the subject will be considered to be a “partial responder”. If there is still CIN 2 and/or 3 present at the 12-Month Visit, the subject will be considered a “non-responder”. The highest grade among the biopsies will be recorded. In addition to the above analysis of subjects who exited after the 12-Month Visit, another analysis may be performed with addition of subjects who exited the study after the 6-Month Visit if histological results (biopsy and/or LEEP) are available at 6 months.

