6.7.1 Procedures for 6-Month Visit

- Perform a physical examination
 - Obtain vital signs
 - Blood pressure

- Heart rate
- Respiratory rate
- Temperature
- Weight
- Ask if any medications have been started or stopped since last visit
- Perform colposcopy
 - Obtain ThinPrep for Pap smear, HPV-DNA and bacterial testing
 - Record the lesion(s), locations on the cervix, image cervix using the colposcope-mounted image capture system (if available)
 - Record in how many cervical quadrants the lesions are visible
- Colposcopy may be performed in the OR if medically necessary. A COVID-19 test may be required per hospital policy prior to intervention in the OR.
- If determined to be necessary by the physician (ONLY in cases where there is a suspicion of progressive disease), obtain punch biopsy and endocervical curettage
- Blood will be drawn for:
 - Immunomonitoring and other analyses (eight 10.0 mL rubber green top sodium heparin tubes unless pregnant then draw only 2 tubes)
 - CBC (to be performed in UAMS clinical laboratory)
 - CMP (be performed in UAMS clinical laboratory)
- If Pap smear and/or biopsy results are suspicious for or consistent with HSIL and if the subject decides not to return for the 12-Month Visit, the optional LEEP visit may be offered as long as a study physician determines doing so would be beneficial.
- If a cervical cancer diagnosis is confirmed prior to being withdrawn from the study, the subject may be offered a hysterectomy if a study physician determines it to be medically necessary.

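### The supplementary comparison with 24.6% (34/138) adds only CIN3 failures to the placebo reference but adds 6-month exits with any histology to the trial arms; the direction of the resulting tilt is not settled

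*Protocol*

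**What the plan says.** Protocol 9.1 sets the main historical comparison on women who complete the 12-Month Visit. The placebo rate for it is the one "which was 29.1% (34 of 117) using binomial test". On scoring it says: "The strict definition of histological response which only considers “complete responders” to be “responders” will be used".

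A second comparison follows. Sections 2.1, 8.1 and 9.1 describe it in nearly the same terms; in 2.1, "another analysis may be performed with addition of subjects who exited the study after the 6-Month Visit if histological results (biopsy and/or LEEP) are available". For the placebo side, 9.1 explains the changed denominator: "As 21 patients in the placebo arm were removed from the study at 3 or 6 months for having persistent biopsy-proven CIN3", and so "the response rate of 24.6% (34 of 138) will be used for this comparison". For the trial side, the added women are "subjects who exited the study after the 6-Month Visit if histological results (biopsy and/or LEEP) are available at 6 months". No sentence limits them to CIN3 or says how a 6-month result is to be scored. Sections 2.1 and 8.1 define complete, partial and non-response on the 12-month quadrant biopsies only.

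Section 6.7.1 governs who has 6-month histology. The instruction for biopsy and curettage is "ONLY in cases where there is a suspicion of progressive disease), obtain punch biopsy and endocervical curettage". The condition for the optional LEEP begins "If Pap smear and/or biopsy results are suspicious for or consistent with HSIL" and adds that the woman has decided not to come back at 12 months.

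SAP section II lists an ITT comparison (34/149, 22.8%) and a per-protocol comparison (34/117, 29.1%). It does not contain the 34/138 comparison.

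**The concern.** A comparison with a fixed historical rate is fair only if the trial arm is assembled by the rule that produced that rate. Here the reference moves from 34/117 to 34/138 by adding women selected because they had failed. Their contribution to the numerator is zero by construction. The trial arms are open to any 6-month histology, so an added woman may count either way.

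A trial woman could leave after a suspicious smear, have a LEEP that shows no CIN, and be counted as a complete responder. That would be a response about six months before the endpoint, on tissue not taken under the four-quadrant rule that 6.9.1 imposes at 12 months. The 21 women added to the reference include no such case.

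At stake is the meaning of an analysis intended to deal fairly with early exits. It is optional and has no stated scoring rule, so both whether it is run and how exits are counted could be settled after the results are known.

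**Working it through.** **Inputs from the documents.** Placebo responders 34; placebo completers 117; placebo women added 21; ITT placebo denominator 149 (all Protocol 9.1). Forty women enrolled per arm, with at least 35 expected to complete (Protocol 1.5.9). Exact two-sided binomial test (SAP II).

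**The plan's own figures.** 34/117 = 29.06%. 117 + 21 = 138 and 34/138 = 24.64%. 34/149 = 22.82%. All three reproduce. The 21 added women are 21/138 = 15.2% of the enlarged reference and contribute no responders.

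**Inputs that must be assumed.** The documents do not give the number of 6-month exits per arm (m) or the share of them without CIN (q). I take m from 0 to 10 and q from 0 to 50%. I also assume that the c completers in a trial arm respond at the placebo rate of 29.06% whatever m is, so that any departure from 24.64% comes from how the arm is assembled and not from a treatment effect.

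**Formula.** Expected arm rate = (c × 0.2906 + m × q) / (c + m). Tilt = that rate minus 24.64%.

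The number of exits in a 40-woman arm that matches the reference is 40 × 21/138 = 6.1, so 34 + 6 is the natural centre. There, with q = 0: (34 × 0.2906 + 0)/40 = 9.88/40 = 24.7%, a tilt of +0.1. With q = 20%: (9.88 + 1.2)/40 = 27.7%, a tilt of +3.1.

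| Completers + exits | q = 0 | q = 20% | q = 33% | q = 50% |
|---|---|---|---|---|
| 35 + 0 | +4.4 | +4.4 | +4.4 | +4.4 |
| 35 + 3 | +2.1 | +3.7 | +4.8 | +6.1 |
| 35 + 5 | +0.8 | +3.3 | +5.0 | +7.0 |
| 34 + 6 | +0.1 | +3.1 | +5.1 | +7.6 |
| 32 + 8 | -1.4 | +2.6 | +5.3 | +8.6 |
| 30 + 10 | -2.8 | +2.2 | +5.5 | +9.7 |

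(Percentage points; positive favours the trial arm.)

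Each credited exit in a 40-woman arm adds 1/40 = 2.5 points. The tilt is zero at q = 7% for 32 + 8 and q = 11% for 30 + 10.

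**Effect on the test.** With n = 40, the smallest count that is significantly high is 18 against 29.1% and 16 against 24.6%. For 34 + 6, the probability of reaching 16 with completers at the placebo rate is 2.0% if all exits fail, 6.2% at q = 20%, 10.7% at q = 33% and 18.4% at q = 50%.

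**The case against.** The strongest answer is that the women added to the trial arms are themselves selected for likely failure. Under 6.7.1 a 6-month biopsy needs suspected progression, and LEEP needs a smear or biopsy pointing to HSIL. Most of them may well be non-responders, much like the 21 placebo women. This stands, and it is why no direction can be claimed. A reader might infer from the rules alone that the comparison is tilted toward the vaccine. The documents do not support that as a settled result: the table runs from -2.8 to +9.7 points, and at 34 + 6 with every exit failing there is almost no tilt.

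A reader might also infer that one benign LEEP could turn a negative historical result positive. Such examples can be built: against 24.6%, 14/37 gives p = 0.083 and 15/37 gives p = 0.034. But that pair sits on the critical boundary for n = 37. At n = 38, moving from 13 to 14 responders changes p only from 0.187 to 0.090. In any case only the optional analysis would move: 14 of 35 completers against 29.1% remains non-significant (p = 0.19) however the exits are scored.

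Two further points have force. Adding the 21 CIN3 failures to the reference is reasonable in itself, because 29.1% leaves them out. And the documents do not say whether any placebo woman left early with regressed histology; 149 - 138 = 11 placebo women are unaccounted for. It would therefore go too far to say that the historical trial never credited an early result. What can be said is that none of the 21 women added to the reference was credited.

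The objection does not remove the mismatch. A suspicious smear can be followed by histology without CIN, and nothing in the plan prevents that result from being counted as a response.

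**Conclusion.** The concern holds as a mismatch of inclusion rules in one supplementary comparison. The reference of 34/138 gains only women with persistent CIN3; the trial arms gain women with any 6-month histology.

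The tilt is about -3 to +10 points over the assumed ranges, and between +0.1 and +7.6 points when the number of exits matches the reference proportion. These figures rest on assumed exit numbers, assumed 6-month histology and a completer rate held at 29.1%.

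The weight is limited. The analysis is optional, it is absent from SAP II, and neither the main comparison with 29.1% nor PepCan versus Candin depends on it. It still merits correction because the stated rule is unmatched, not merely short of detail, and matching it needs only wording.

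**What to change.** In Protocol 2.1, 8.1 and 9.1, apply one rule to both sides. Suggested text: *For the comparison with 34/138, only women who exit at 6 months with persistent biopsy-proven CIN3 are added, as non-responders. A 6-month biopsy or LEEP without CIN is not credited as a response.* Tabulate all 6-month exits and their histology by arm. As a conservative sensitivity analysis, score every 6-month exit as a non-responder. This should not be the main rule, since the reference added CIN3 only, and with 8 to 10 exits it would lean against the vaccine by 1.4 to 2.8 points on the assumptions above. If the comparison is kept, SAP II should carry it.

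Alternatively, delete the 24.6% comparison from the protocol, in line with SAP II, and rely on the ITT comparison with 34/149 for early exits.

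The cost is a wording change and a supplementary rate that may be slightly less favourable. One limit remains if the comparison is kept: placebo women with persistent CIN3 were removed, whereas trial women leave by choice, so the number added may still differ from the reference proportion (35 + 3, all failing, leaves +2.1 points). The report should say so.

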9.2 ASSESSING SAFETY: SUMMARY OF ADVERSE EVENTS

Subjects who received at least one dose of PepCan or Candin® will be included in safety assessments. Results will be tabulated as shown in Table 2. The type of adverse reactions, the CTCAE grades, and whether the reactions are vaccine-related will be indicated.

9.3 ASSESSING IMMUNOLOGICAL RESPONSE AND VIRAL CLEARANCE

9.3.1 Immunological Response

9.3.1.1 CD3 T-Cell Response to HPV

As described above, a paired t-test for paired samples will be performed in order to compare each region with increased positivity index after 2 or 4 injections compared to pre-vaccination, as shown in Fig. 3 for the PepCan arm. An analogous analysis will be performed for the Candin® arm, and the number of regions with statistically significant increases will be compared between the two treatment arms to elucidate the additive effects of the E6 peptides.

A correlation between CD3 T-cell response to HPV and clinical response will be examined by drawing a contingency table for a number of subjects with at least one region with statistically significant increase to E6 in "responders" and "non-responders" separately for the PepCan and Candin® groups. Fisher's exact test will be used.

9.3.1.2 Circulating Immune Cells

The changes in percentage of circulating immune cells such as Th1, Th2, Treg, and MDSC will be compared after 2, 6 months after 4 vaccinations, and 12 months after 4 vaccinations with baseline as shown in Fig. 4. Paired t-test and one-way ANOVA will be performed to determine statistical significance separately for the PepCan and Candin® groups.

The differences between the percentages of each circulating immune cell types will be compared between the "responders" and the "non-responders" at pre-vaccination, post-2 vaccination, 6 months after post-4 vaccination, and 12 months after post-4 vaccination using Wilcoxon rank-sum test separately for the PepCan and Candin® groups.

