1.5.11.2 Rationale for Measuring Circulating Immune Cells

The level of circulating immune cells, including Th1 cells, Th2 cells, regulatory T-cells (Treg), and myeloid-derived suppressor cells (MDSC), will be assessed before vaccination, after 2 vaccinations, 6 months after 4 vaccinations, and 12 months after 4 vaccinations. The data from the Phase I clinical trial indicated that PepCan may increase Th1 responses ($p=0.02$) and decrease Th2

responses resulting in increased effector immune activity (**Fig. 4**). Whether the levels of these circulating immune cells can be used to predict vaccine efficacy in terms of clinical response and viral clearance will be investigated. Vaccine effects on these factors will also be examined throughout the study (i.e., 6 and 12 months instead of 3 months).

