1.5.13 Rationale for Adding a Candin® Arm

The results of the dose-escalation portion of the Phase I clinical trial showed similar rates of clinical responses in subjects with HSILs associated (4 of 9 or 44%) and not associated (8 of 14 or 57%) with HPV 16 suggesting that *de novo* immune stimulation presumably from Candin® plays a major role. Therefore, Candin® only treatment arm will be added to compare efficacy between PepCan and Candin®.

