4.2 RANDOMIZATION TO TREATMENTS

The study randomization schematic will be constructed by the study Statistician. Randomization will occur after Subject eligibility for vaccinations has been confirmed. Subjects will be randomized in a 1:1 ratio to PepCan or Candin® alone. Randomization will be done in book form by Research Pharmacy.

Fig. 6 Schematic presentation of study visits scheduled for the Phase II clinical trial of our HPV therapeutic vaccine. Colpo, colposcopy, Bx, biopsy, ECC, endocervical curettage, LEEP, loop electrosurgical excision procedure. [†]These blood tests are for clinical analyses only. ^{*}These blood tests are for scientific analyses only. Blood tests may be drawn as needed for clinical and/or scientific analyses during any optional visit.

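### Circulating immune cells are tested for change only within each arm; no PepCan versus Candin comparison is planned, so a result significant in one arm only may be misread as a peptide effect

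*Protocol*

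**What the plan says.** Protocol section 9.3.1.2 plans two analyses of circulating immune cells.

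- **Change from baseline.** "The changes in percentage of circulating immune cells such as Th1, Th2, Treg, and MDSC will be compared" with baseline after two vaccinations and at 6 and 12 months after the fourth. The method is: "Paired t-test and one-way ANOVA will be performed to determine statistical significance separately for the PepCan and Candin® groups".
- **Responders against non-responders** at each time point, "using Wilcoxon rank-sum test separately for the PepCan and Candin® groups".

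The ANOVA factor is not named. Because the ANOVA is run separately by arm, it cannot be treatment.

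The section just before it, 9.3.1.1, handles the E6-specific T-cell response differently: the "number of regions with statistically significant increases will be compared between the two treatment arms to elucidate the additive effects of the E6 peptides". Between-arm tests are also planned for histological response (Protocol 9.1, SAP II) and for common treatment-related adverse events (SAP III).

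For circulating cells, Protocol 1.5.11.2 states the aim as "Vaccine effects on these factors will also be examined throughout the study". Sections 2.3, 2.4, 8.3.2.1 and 9.5 contain no arm comparison of these cells. The SAP's analysis sections cover baseline characteristics, efficacy and safety only; it mentions immunomonitoring as sample collection. Allocation is stated in 4.2: "Subjects will be randomized in a 1:1 ratio to PepCan or Candin® alone".

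**The concern.** A change from baseline over a year or more combines whatever the injections do with time and the course of the disease. Within one arm these cannot be separated. The other randomised arm goes through the same time and follow-up, so the difference between arms isolates what the peptides add to Candin. Section 9.3.1.2 does not estimate that difference.

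The plan will instead produce two columns of p-values, one per arm. The natural way to read them is to note where PepCan is significant and Candin is not. That reading is invalid: two arms with identical true changes will often fall on opposite sides of 0.05. The peptides are the only planned difference between the arms, and 9.3.1.1 already interprets an arm difference as their contribution, so the risk of this misreading is concrete.

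The likely origin is visible. Section 9.3.1.2 takes Fig. 4 from Phase I as its template, and Phase I was a single-arm trial (1.4.1), where only within-group tests were possible.

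**Working it through.** **Plan's own figure.** There is no power or sample-size statement for circulating cells. The number per arm comes from section 1.5.9: 40 enrolled so that at least 35 complete, with 91% power for histological regression of 60% against 29% (34 of 117). That figure reproduces at 91.7% (two-sided pooled normal test, 35 against 117), but it concerns another outcome. Only n = 35 is taken from it.

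**Assumed inputs** (not in the documents): the same true change d in both arms, in units of the cross-sectional SD; correlation r between baseline and follow-up; normal data; two-sided 0.05.

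**Formulas**
- Standardised paired change: dz = d / √(2(1 − r)).
- Within-arm power P: paired t-test, noncentral t with 34 df and noncentrality dz × √35.
- Exactly one arm significant: 2P(1 − P). PepCan only: P(1 − P).

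**Worked example.** For d = 0.3 and r = 0.5, dz = 0.3, P = 0.407, and 2 × 0.407 × 0.593 = 48%. PepCan only is 24%.

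| d (SD) | r | dz | P | Exactly one arm | PepCan only |
|---|---|---|---|---|---|
| 0 | any | 0 | 0.050 | 9.5% | 4.8% |
| 0.1 | 0.5 | 0.100 | 0.089 | 16% | 8% |
| 0.1 | 0.7 | 0.129 | 0.115 | 20% | 10% |
| 0.2 | 0.5 | 0.200 | 0.210 | 33% | 17% |
| 0.2 | 0.7 | 0.258 | 0.318 | 43% | 22% |
| 0.3 | 0.5 | 0.300 | 0.407 | 48% | 24% |
| 0.3 | 0.7 | 0.387 | 0.605 | 48% | 24% |
| 0.4 | 0.5 | 0.400 | 0.633 | 46% | 23% |
| 0.4 | 0.7 | 0.516 | 0.843 | 26% | 13% |
| 0.5 | 0.5 | 0.500 | 0.820 | 30% | 15% |
| 0.5 | 0.7 | 0.645 | 0.960 | 8% | 4% |
| 0.6 | 0.5 | 0.600 | 0.932 | 13% | 6% |
| 0.6 | 0.7 | 0.775 | 0.994 | 1% | 1% |

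The ceiling of 2P(1 − P) is 50%, reached when P = 0.5; d = 0.3 with r = 0.6 sits almost exactly there. Simulation of 200,000 trials at dz of 0, 0.2, 0.336 and 0.5 gave 9.4%, 33.2%, 49.8% and 29.7%, in line with the formula.

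**Direct between-arm test under the same equal changes.** The two-sample t-test on change scores rejected in 5.0% of the same simulated trials. Baseline-adjusted ANCOVA also rejected in about 5% (40,000 trials, d = 0.3, r of 0.5 and 0.7).

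**Several comparisons.** Four cell types at three post-baseline times make 12 comparisons. With no change in either arm, and treating them as independent (an assumption), the expected number of one-arm-only results is 12 × 0.095 = 1.1. The chance of at least one is 1 − 0.905^12 = 70%.

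**Is the direct test informative at this size?** Take true changes of 0.6 SD for PepCan and 0.1 SD for Candin, a difference of 0.5 SD. ANCOVA noncentrality is 0.5/√(1 − r²) × √(35/2), which is 2.42 at r = 0.5 and 2.93 at r = 0.7. Power is about 66% and 81% to 82%.

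**The case against.** **No passage says a one-arm result will be credited to the peptides.** That is right. A reader might infer that the plan intends this reading, but the documents support only that it may happen.

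**The peptide increment is not the stated tertiary question for these cells.** This also stands. Sections 1.1 and 2.3 ask about immunological response in general. The increment is named only for T-cell regions, where the arms are compared, and the Candin arm was justified on clinical grounds: "Candin® only treatment arm will be added to compare efficacy between PepCan and Candin". The sentence in 1.5.11.2 goes on to speak of later time points, and 2.4 speaks of effects over time, which within-arm summaries do describe. The gap therefore concerns the comparison between arms, not everything the protocol asks of these cells.

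**The either-direction rate overstates the harm.** Only PepCan-significant with Candin-not could be read as a peptide effect, and under equal changes that is half the total. The middle of the assumed range is also where discordance peaks; at zero or large changes it is much lower. Both rates and the full range are shown above for that reason.

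**The randomised comparison may not be clean.** Section 4.4 allows new women to be assigned to Candin without randomisation, and women in mid-course to be switched to Candin, if peptides run out. If that happened, the contrast needs a population rule. It does not remove the case for a contrast.

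**It is one part of a tertiary outcome, and the analysis could be added later.** True, but a contrast chosen after the within-arm p-values are known is weaker than one specified now.

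A reader might also conclude that the trial never compares its arms. It does, for histology, common adverse events and T-cell region counts.

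**Conclusion.** The point holds for circulating immune cells only. Section 9.3.1.2 tests change within each arm, no PepCan versus Candin comparison of these cells is planned anywhere, and the SAP does not supply one. A randomised comparator exists and is not used for this outcome.

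Under the assumed 0.2 to 0.4 SD change and correlation of 0.5 or 0.7, arms that truly change alike would show a one-arm-only result in roughly a quarter to a half of comparisons. About half of those would favour PepCan. With no true change the rate is 9.5%, and at 0.5 SD it is 8% to 30%. The effect sizes, SDs and correlations are assumptions; the failure of the logic does not depend on them, only its frequency does.

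The change is worth making because it is cheap and improves a stated method. It does not touch the primary efficacy conclusion.

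**What to change.** In 9.3.1.2 and in a new SAP section, specify for each cell type and post-baseline visit the baseline-adjusted PepCan minus Candin difference with a 95% CI. ANCOVA at each visit is enough; a repeated-measures model with arm, visit, arm-by-visit and baseline is an alternative. Name this the between-arm vaccine-effect analysis and keep the within-arm changes as description.

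Two matters need settling first.

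- **Sampling times.** Section 8.3.2.1 lists Visits 1, 3 and 5, and times before vaccination, after two and after four injections. Sections 2.3 and 9.3.1.2 list baseline, after two, and 6 and 12 months after the fourth. Appendix 1 has no column called Visit 5. These must be reconciled before the visits in the model can be defined.
- **Population.** Restrict the contrast to randomised women, or flag those assigned or switched to Candin during an interruption under 4.4 and show the result with and without them.

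The cost is some SAP text, minor programming and the two clarifications. No new samples or visits are needed. The price is a little extra analysis on a tertiary outcome, with modest power (about 66% to 82% for a 0.5 SD difference), so the interval matters more than the p-value.
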